12.3 Safety Monitoring

Assuring patient safety is an essential component of this protocol. Each participating investigator has primary responsibility for the safety of the individual participants under his or her care. The investigators will determine daily if any adverse events occur during the period from enrollment through **study day 4,(which is** 72 hours after completion of the study product infusion, or hospital discharge, whichever occurs first, and will determine if adverse events are related to study procedures. Adverse events are not required to be reported to the IRB unless the investigator feels the adverse event **was related** to study infusion or study procedures.

The following adverse events will be collected in the adverse event case report forms:

- Serious adverse events (as defined in protocol section 12.2 of this protocol) that are study related (or of uncertain relationship) or occur within 72 hours of the study infusion
- Non-serious adverse events that are study procedures or of uncertain relationship
- Events leading to permanent discontinuation of study infusion (which, by definition, are study related)

The protocol for reporting adverse events in the trial's electronic data capture system are summarized in Table 4.

Table 4. Protocol for reporting adverse events

Type of Adverse Event	Time for Recording in the EDC
Serious, study related	24 hours
Serious, not study related and within 72 hours of infusion	72 hours
Serious, not study related and after 72 hours following	Recording in the EDC is not required
Not serious, study related	72 hours
Not serious, not study related	Recording in the EDC is not required

Study-specific clinical outcomes (Primary, Secondary and Safety Outcomes and Assessments During the Study), including serious outcomes such as organ failures and death, are systematically recorded in the case report forms and are exempt from adverse event reporting unless the investigator deems the event to be related to the administration of study plasma or the conduct of study procedures (or of uncertain relationship).

After randomization, adverse events must be evaluated by the investigator. If the adverse event is judged to be reportable, as outlined above, then the investigator will report to the Medical Monitor for assessment of the potential relatedness of each adverse event to the study treatment or protocol procedure via electronic data entry. Investigators will assess if there is a reasonable possibility that the study procedure caused the event. Investigators will also consider if the event is unexpected. Unexpected adverse events are events not listed in the study protocol or investigator's brochure. Investigators will also determine if adverse events are unanticipated given the patient's clinical course, previous medical conditions, and concomitant medications.

If a patient's treatment is discontinued as a result of an adverse event, study site personnel must also report the circumstances and data leading to discontinuation of treatment in the adverse event case report forms. Additional information about adverse event reporting is included in Appendix B.

12.4 Medical Monitor

The relationship or attribution of an adverse event to the study therapy will be initially determined by the site investigator and recorded on the appropriate eCRF. Final determination of attribution for safety reporting will be determined by the independent medical monitor. The Medical Monitor may escalate reported events to the DSMB chair as appropriate per the DSMB charter.

The activities of the Medical Monitor will include:

- Being on call for investigators to report and discuss AEs and SAEs
- Reviewing safety data delivered to the DSMB and any safety reports
- Attending DSMB meetings to participate in discussions about safety and AEs
- Participation in discussions about unblinding study team members to study drug allocation to facilitate safe treatment of study participants

12.5 Data and Safety Monitoring Board (DSMB)

The principal role of the DSMB is to assure the safety of participants in the trial. They will regularly monitor data from this trial, review and assess the performance of its operations, and make recommendations to the study team. DSMB activities include:

- Review of adverse events
- Interim results of the study for evidence of efficacy or adverse events
- Possible early termination of the trial because of new external information, early attainment of study objectives, safety concerns, or inadequate performance
- Possible modifications in the clinical trial protocol
- Performance of individual centers

The DSMB is selected by the study team for their expertise in relevant fields. The DSMB reviews all protocols for safety. The DSMB will consist of members with expertise in acute lung injury, transfusion medicine, biostatistics, ethics, and clinical trials. Appointment of all members is contingent upon the absence of any conflicts of interest. All the members of the DSMB are voting members. An unblinded statistician and coordinating center personnel will be responsible for the preparation of all DSMB and adverse event reports and may review unblinded data. The DSMB will develop a charter and review the protocol and sample consent form during its first meeting. Subsequent DSMB meetings will be scheduled in accordance with the DSMB Charter. When appropriate, conference calls may be held in place of face-to-face meetings. Recommendations to end, modify, or continue the trial will be prepared by the DSMB. Recommendations for major changes, such as stopping the trial, will be communicated to the executive committee/sponsor-investigator.

APPENDICES

Appendix A: Schedule of Events

	Screening & Consent	Baseline & Transfusion	Follow-up									
			2	3	4	5	6	7	8 ¹	15 ¹	29 ¹	
Day	1 or before	1										
Confirm eligibility, including positive SARS-CoV-2 test	x											
Informed consent	x											
Randomization		x										
Demographic and Medical history		x										
ABO type (complete on study protocol if clinical results not available; follow institutional policy)		x ⁴										
Study infusion		x ²										
Record vital signs		x	x ³	x ³	x ³	x ³	x ³	x ³	x ³			
COVID-19 symptom screen		x										
Concomitant medications		x										
Assessment with COVID-19 7-point Ordinal Clinical Progression Outcomes Scale		x	x ³	x ³	x ³	x ³	x ³	x ³	x	x	x	
Collect data for later calculation of SOFA score		x	x ³									
Record new medical conditions		x	x ³	x ³	x ³	x ³	x ³	x ³	x	x	x	
Adverse event monitoring		x	x ³	x ³	x ³							
CRP (complete on study protocol if clinical results not available)		x ⁴										
CBC and CMP (complete on study protocol if clinical results not available)		x ⁴	x ^{3,4}									
Blood for COVID-19 titer testing		x ⁵	x ³									
Record the results of a clinically obtained CBC and CMP (only if clinically available)									x			

¹ If patient is discharged before the follow-up visits on Day 8, 15, and 29, follow-up study activities on these days will be performed via phone calls. Day 8 call window will be Day 8 through 14. The Day 15 call window will be Day 15 through 22. The Day 29 call window will be Day 29 through 36

² Study infusion will be monitored per site institutional transfusion policy.

³ Only performed if hospitalized.

⁴ Only if not performed as part of standard of care.

⁵ Must be drawn prior to study infusion.

Appendix B: Adverse Event Reporting and Unanticipated Events

Investigators will report all serious adverse events that occur within 72 hours of study infusion to the Vanderbilt Coordinating Center (VCC) regardless of relatedness. Serious adverse events that are determined to be related to study procedures (regardless of timing related to study infusion) will be reported to the VCC within 24 hours. Hence, all serious adverse events judged to be related or possibly related to study procedures will be reported within 24 hours (Figure 2). The VCC will then notify the single Institutional Review Board (sIRB).

The Medical Monitor will work collaboratively with the reporting investigator to determine if a serious adverse event has a reasonable possibility of having been caused by the study infusion or study procedure, as outlined in 21 CFR 312.32(a)(1), and below. The Medical Monitor will be unblinded and will also determine if the event is unexpected for convalescent plasma. An adverse event is considered “unexpected” if it is not listed in the investigator brochure or the study protocol [21 CFR 312.32(a)]. If a determination is made that a serious adverse event has a reasonable possibility of having been caused by a study procedure or the study infusion, it will be classified as a suspected adverse reaction. If the suspected adverse reaction is unexpected, it will be classified as a serious unexpected suspected adverse reaction (SUSAR).

The VCC will report all unexpected deaths, serious and treatment related adverse events, and SUSARs to the DSMB and sIRB within 7 days after receipt of the report from a clinical site. A written report will be sent to the, DSMB, FDA, and the sIRB within 15 calendar days. The DSMB will also review all reported adverse events and clinical outcomes during scheduled interim analyses. The VCC will distribute the written summary of the DSMB’s periodic review of reported adverse events to the sIRB.

B.1. Unanticipated Problems (UP)

Investigators must also report Unanticipated Problems, regardless of severity, associated with study procedures within 24 hours. An unanticipated problem is defined as follows: any incident, experience, or outcome that meets all the following criteria:

- Unexpected, in terms of nature, severity, or frequency, given the research procedures that are described in the protocol-related documents, such as the sIRB-approved research protocol and informed consent document; and the characteristics of the subject population being studied.
- Related or possibly related to participation in the research; possibly related means there is a reasonable possibility that the incident, experience, or outcome may have been caused by the procedures involved in the research.
- Suggests that the research places subjects or others at a greater risk of harm (including physical, psychological, economic, or social harm) than was previously known or recognized.

B.2. Determining Relationship of Adverse Events to Study Infusion or Study Procedures

Investigators will be asked to grade the strength of the relationship of an adverse event to study infusion or study procedures as follows:

- Definitely Related: The event follows: a) A reasonable, temporal sequence from a study procedure; and b) Cannot be explained by the known characteristics of the patient’s clinical state or other therapies; and c) Evaluation of the patient’s clinical state indicates to the investigator that the experience is definitely related to study procedures.
- Probably or Possibly Related: The event should be assessed following the same criteria for “Definitely Associated”. If in the investigator’s opinion at least one or more of the criteria are not present, then “probably” or “possibly” associated should be selected.
- Probably Not Related: The event occurred while the patient was on the study but can reasonably be explained by the known characteristics of the patient’s clinical state or other therapies.
- Definitely Not Related: The event is definitely produced by the patient’s clinical state or by other modes of therapy administered to the patient.

- Uncertain Relationship: The event does not meet any of the criteria previously outlined.

B.3. Clinical Outcomes that may be Exempt from Adverse Event Reporting

Study-specific outcomes of acute respiratory infection, COVID-19, and critical illness will be systematically collected for all patients in both study groups and are exempt from adverse event reporting unless the investigator considers the event to be Definitely Probably, or Possibly Related (or of an Uncertain Relationship) to the study infusion or study procedures. Examples of study-specific clinical outcomes include:

- Death not related to the study procedures
- Neurological events
 - Ischemic stroke
- Cardiovascular events
 - Receipt of vasopressors
 - Cardiomyopathy
 - Myocardial infarction
 - Cardiac arrest
 - Deep vein thrombosis
 - Pulmonary embolism
- Respiratory events
 - Hypoxemia requiring supplemental oxygen
 - Acute respiratory distress syndrome
 - Receipt of mechanical ventilation
 - Receipt of extra-corporeal membrane oxygenation
- Gastrointestinal events
 - Elevation of aspartate aminotransferase or alanine aminotransferase
- Renal events
 - Acute kidney injury
 - Receipt of renal replacement therapy
- Hematologic or coagulation events
 - Neutropenia, lymphopenia, anemia, or thrombocytopenia

Note: A study-specific clinical outcome may also qualify as a reportable adverse event. For example, a cardiac arrest that the investigator considers Definitely or Possibly Related to the study infusion would be both recorded as a study-specific clinical outcome and reported as a Serious and Definitely or Possibly Related Adverse Event.

B.4. Decision tree for determining if an adverse event is reportable

Figure 2. Decision tree for determining if an adverse event is reportable

[figure not shown]

Figure adapted from Ranieri VM, Thompson BT, Barie PS et al. Drotrecogin alfa (activated) in adults with septic shock. N Engl J Med. 2012 May 31;366 (22):2055-64. PMID: 22616830.

The key features of the trial are summarized in detail in the study protocol. The following table restates some of the key study features from the protocol.

Feature	Description
Study Design	Multicenter, blinded, placebo-controlled randomized clinical trial
Randomization	Eligible participants will be randomized 1:1 to convalescent plasma versus lactated Ringer's solution with multivitamins. Randomization will be completed in permuted blocks and stratified by site, gender, and age.
Blinding	Patients and outcome assessors will be blinded to group assignment.
Intervention group treatment	1 unit (200–399 ml) of SARS-CoV-2 convalescent plasma infused intravenously
Control group treatment	250 ml of Lactated Ringer's with multivitamins, which visually resembles plasma, infused intravenously
Inclusion Criteria	
1. Age greater than or equal to 18 years of age2. Currently hospitalized or in an emergency department with anticipated hospitalization3. Symptoms of acute respiratory infection, defined as one or more of the following:
a. Coughb. Chills, or a fever (greater than 37.5° C or 99.5° F)c. Shortness of breath, operationalized as a patient having any of the following:
i. Subjective shortness of breath reported by a patient or surrogate.ii. Tachypnea with respiratory rate of greater than 22 breaths per minuteiii. Hypoxemia, defined as SpO₂ less than 92% on room air, new receipt of supplemental oxygen to maintain SpO₂ greater than or equal to 92%, or increased supplemental oxygen to maintain SpO₂ greater than or equal to 92% for a patient on chronic oxygen therapy4. Laboratory-confirmed SARS-CoV-2 infection within the past 14 days
Exclusion Criteria	
1. Prisoner2. Unable to randomize within 14 days after onset of acute respiratory infection symptoms3. Patient, legal representative, or physician not committed to full support (Exception: a patient who will receive all supportive care except for attempts at resuscitation from cardiac arrest will not be excluded.)4. Inability to be contacted on Day 29-36 for clinical outcome assessment5. Receipt of COVID-19 convalescent plasma or pooled immunoglobulin in the past 30 days6. Contraindications to transfusion or history of prior reactions to transfused blood products

	
7. Plan for hospital discharge within 24 hours of enrollment
 
8. Previous enrollment in this trial
 
9. Enrollment in another clinical trial evaluating monoclonal antibodies, convalescent plasma, or another passive immunity therapy

Sample Size	1000
Primary Outcome	
COVID-19 7-point Ordinal Clinical Progression Outcomes Scale on Study Day 15:
 
 1. Not hospitalized with resumption of normal activities. 2. Not hospitalized, but unable to resume normal activities. 3. Hospitalized, not on supplemental oxygen. 4. Hospitalized, and on supplemental oxygen. 5. Hospitalized, on nasal high-flow oxygen therapy, noninvasive mechanical ventilation, or both 6. Hospitalized, on ECMO, invasive mechanical ventilation, or both. 7. Death
Secondary Outcomes	
 • All-location, all-cause 14-day mortality (assessed on Study Day 15) • All-location, all-cause 28-day mortality (assessed on Study Day 29) • Survival through 28 days • Time to hospital discharge through 28 days • Time to recovery (defined as time from randomization to the earlier of final oxygen receipt in the hospital or hospital discharge). • COVID-19 7-point Ordinal Clinical Progression Outcomes Scale on Study Day 3, 8, and 29 • Oxygen-free days through Day 28 • Ventilator-free days through Day 28 • Vasopressor-free days through Day 28 • ICU-free days through Day 28 • Hospital-free days through Day 28 • Endpoints developed in the course of the pandemic
Safety Outcomes	
 • Acute kidney injury • Receipt of renal replacement therapy • Documented venous thromboembolic disease (DVT or PE) • Documented cardiovascular event (myocardial infarction or ischemic stroke) • Transfusion reaction • Transfusion related acute lung injury (TRALI) • Transfusion associated circulatory overload (TACO) • Transfusion related infection
Primary AIM	
Assess if the treatment intervention improves the day 15 endpoint compared to the control arm
 
It is hypothesized that among adults hospitalized with COVID-19, administration of convalescent plasma will improve clinical status 14 days after randomization.

Inference approach	The primary point of inference will be the likelihood ratio and corresponding support interval for the covariate adjusted treatment effect odds ratio. Likelihood ratios more extreme than 7 (or 1/7) will be interpreted as sufficient evidence to assert efficacy. The odds ratio will be estimated with a cumulative probability ordinal regression model with logit link.
Planned Interim Analyses	There are 3 interim analyses for safety endpoints, and a final analysis of efficacy endpoints. The safety interim analyses will occur after 15 days of follow-up is completed for the first 150, 450, and 750 patients. The final analysis will occur after follow-up and data lock is complete for all enrolled subjects.
Planned Reporting Triggers	There are no planned reporting triggers.
Planned stopping rules	The trial will end for safety if a one-sided test of the difference in risk of mortality between control and intervention arms is significant at the alpha = 0.1 level. The mortality stopping rule will be evaluated at the 3 interim analyses described above.
Type I error rate	The combination of a 1/7 likelihood ratio threshold and the safety stopping rule result in a simulated type I error rate of 0.02
Power	The minimal detectable effect at 80% power is an OR of 0.73.

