8.2 Planned interim analyses for mortality

At each interim analysis, the difference in mortality risk will be calculated, and the one-sided hypothesis that mortality risk in the intervention arm exceeds the mortality risk in placebo will be compared to the null hypothesis of equal mortality risk. The trial will be stopped if the likelihood ratio exceeds the threshold listed below. Generally, the level of evidence required to stop a study for safety concerns is less than the level of evidence required to assert efficacy of the intervention. Likewise, there is not the same level of concern for type 1 error control for safety outcomes as there is for efficacy endpoints; however, the threshold values were selected so that the trial-wise risk of ending early for mortality is 0.1 if the treatment is equivalent to placebo. To provide context for the LR thresholds listed in the table below, we have also provided α_N , the p-value threshold which approximates the LR threshold if the p-value were calculated from a likelihood ratio test.

N	LR Threshold	α_N
150	6.3	0.0275
450	4.0	0.0479
750	3.3	0.0612

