The trial will be stopped if the likelihood ratio exceeds the threshold listed below. Generally, the level of evidence required to stop a study for safety concerns is less than the level of evidence required to assert efficacy of the intervention. Likewise, there is not the same level of concern for type 1 error control for safety outcomes as there is for efficacy endpoints; however, the threshold values were selected so that the trial-wise risk of ending early for mortality is 0.1 if the treatment is equivalent to placebo ($\Delta = 0$). To provide context for the LR thresholds listed in the table below, we have also provided α_N , the p-value threshold which approximates the LR threshold if the p-value were calculated from a likelihood ratio test.

N	LR Threshold	α_N
150	6.3	0.0275
450	4.0	0.0479
750	3.3	0.0612

3. Analysis plan for primary endpoint

The data from the clinical trial will be analyzed after follow-up and data lock is completed for all study subjects. The analysis will be intent-to-treat, meaning that patients will be analyzed according to the randomization schedule regardless of the treatment administered. The main result will be an estimate of the treatment effect odds ratio, its likelihood ratio when compared to the null, and the corresponding 1/7 likelihood support interval, all of which will be estimated from a cumulative probability ordinal regression model (CPM) with logit link. The marginal likelihood function for the treatment effect parameter will be the asymptotic regression coefficient distribution; specifically, it will be the normal distribution density function with mean and standard deviation equal to the regression estimates. Likelihood ratios more extreme than 7 will be interpreted as sufficient evidence to assert efficacy. In order to increase study power, the following variables will also be included into the regression:

1. Treatment (1 parameter)
2. Age (2 parameters, restricted cubic spline)
3. Sex (1 parameter)
4. Baseline SOFA score (1 parameter, linear term)
5. Baseline COVID-19 7-point Ordinal Clinical Progression Outcomes Scale score (possible range:3-6) (2 parameters, quadratic)
6. Time from symptom onset in days (2 parameter, non-linear term)
7. Site indicator variables (either as a main effect or as a random effect, depending on the number of sites enrolling patients)

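### The SAP gives two different mortality stopping rules; as written, the summary-table rule doubles the false-stop risk from 0.10 to about 0.20

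*SAP*

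**What the plan says.** The row on planned stopping rules in the SAP's opening summary table compares mortality in the two groups with a one-sided test and stops the trial for safety when the result "is significant at the alpha = 0.1 level. The mortality stopping rule will be evaluated at the 3 interim analyses". The row on interim analyses fixes the timing: "The safety interim analyses will occur after 15 days of follow-up is completed for the first 150, 450, and 750 patients". The stopping row gives no likelihood ratio threshold and no level per look. It does not say that 0.1 is a trial-wise figure, and it does not point to Section 2.

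SAP Section 2 (planned interim analyses for mortality) sets a likelihood ratio rule in the direction of harm. Its table lists sample size, threshold and approximate p-value level (alpha_N): "150 6.3 0.0275" at the first look, "450 4.0 0.0479" at the second and "750 3.3 0.0612" at the third. It explains the choice: "the threshold values were selected so that the trial-wise risk of ending early for mortality is 0.1 if the treatment is equivalent to placebo".

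Protocol 8.2 carries the same table and the same rule: "The trial will be stopped if the likelihood ratio exceeds the threshold listed below". The matching row of Protocol Table 1 (Section 8.1) also uses the likelihood ratio rule and mentions no test at 0.1. The SAP introduces its summary table as a restatement of protocol features, but this row does not restate the protocol's row.

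**The concern.** The number 0.1 has two meanings. In SAP Section 2 it is the probability, over all three looks together, of stopping a trial in which plasma and placebo have equal mortality. In the summary row it is the significance level of a test that is then applied at three analyses. A test at 0.1 carried out three times on accumulating data has an overall false-stop risk above 0.1.

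This is the only formal stopping rule in the trial. A monitoring board or unblinded statistician working from the summary table would use a much looser boundary than one working from Section 2. The SAP also attributes its simulated operating characteristics to the stopping rule, including the efficacy type I error of 0.02, so there has to be one identified rule.

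**Working it through.** **Inputs from the documents.** Looks at N = 150, 450 and 750; 1:1 allocation; one-sided test for harm; likelihood ratio (LR) thresholds 6.3, 4.0 and 3.3; alpha_N 0.0275, 0.0479 and 0.0612; stated trial-wise risk 0.1; summary-row level 0.1. The documents give no mortality rate, so every rate below is an assumption.

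**Step 1: are the two rules on the same scale?** Use z = √(2 ln LR) and one-sided p = 1 − Φ(z).

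| N | LR threshold | z | One-sided p | Stated alpha_N |
|---|---|---|---|---|
| 150 | 6.3 | 1.919 | 0.0275 | 0.0275 |
| 450 | 4.0 | 1.665 | 0.0479 | 0.0479 |
| 750 | 3.3 | 1.545 | 0.0611 | 0.0612 |

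The match is exact apart from rounding in the last row. Two-sided values (0.055, 0.096, 0.122) do not match. The tabulated levels are therefore one-sided and directly comparable with the one-sided 0.1 in the summary row.

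In the other direction, one-sided 0.1 is z = 1.2816, and LR = exp(1.2816²/2) = 2.27. That is below all three listed thresholds.

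**Step 2: trial-wise false-stop risk under equal mortality.** The three test statistics are treated as jointly normal with correlation √(Nᵢ/Nⱼ), and the risk is 1 − P(no crossing).

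| Cumulative risk after | SAP Section 2 thresholds | One-sided 0.1 at each look |
|---|---|---|
| Look 1 | 0.0275 | 0.100 |
| Look 2 | 0.066 | 0.163 |
| Look 3 | 0.0994 | 0.2015 |

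The Section 2 column reproduces the stated 0.1. The other column spends the whole 0.1 at the first look and ends at 0.2015 / 0.0994 = 2.03 times the Section 2 figure. Treating the looks as independent (0.271) or adding the levels (0.30) would overstate the risk.

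**Step 3: simulation check.** Binomial deaths, 500,000 trials per setting, equal mortality assumed at 5% to 25%. The alpha_N rule gives 0.099 to 0.104, the LR rule 0.101 to 0.108, and 0.1 at each look 0.204 to 0.211. The doubling hardly depends on the assumed rate.

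**Step 4: stopping probability when mortality differs (assumed rates).**

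| Control → plasma mortality | SAP Section 2 thresholds | One-sided 0.1 at each look |
|---|---|---|
| 10% → 8% | 2.1% | 6.8% |
| 15% → 13% | 2.7% | 8.1% |
| 25% → 23% | 3.4% | 9.7% |
| 15% → 20% | 65% | 77% |

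The looser rule detects harm more often. It also stops a beneficial treatment about three times as often.

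**Step 5: one look where the rules disagree.** Take N = 150 with 75 per arm and 18 deaths on plasma against 11 on placebo. The difference is 7/75 = 0.0933 and the pooled risk is 29/150 = 0.193. Then z = 0.0933 / √(0.193 × 0.807 × 2/75) = 1.45, one-sided p = 0.074 and LR ≈ exp(1.447²/2) = 2.85. The summary row says stop, because 0.074 < 0.1. Section 2 says continue, because 2.85 < 6.3.

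**The case against.** The best defence is that the row is shorthand. It does not say that 0.1 applies at each look, and Section 2 uses the same figure as the trial-wise risk. On that reading the false-stop risk stays at 0.10 and the row is only an incomplete summary of a rule that is fully specified in SAP Section 2 and Protocol 8.2. That is probably how the wording arose. But the row describes a test significant at 0.1 and then says the rule is evaluated at three analyses, which in plain reading is a test at 0.1 each time. Even on the generous reading it gives no threshold that could be applied at a look. Both readings need the same correction.

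Three further points stand as limits:

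- The mortality rule can only end the trial before the efficacy analysis, so the looser version does not by itself raise the efficacy type I error of 0.02.
- The monitoring board may stop or modify the trial at any time, and the SAP openly accepts weaker error control for safety. This softens the practical effect but does not settle which boundary the board is to be shown.
- No figure in the plan is miscalculated. Section 2 is correct on its own terms, and the fault is the conflict between it and the summary row.

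**Conclusion.** The concern holds. The SAP's summary row contradicts SAP Section 2 and Protocol 8.1 and 8.2 on the boundary of the only formal stopping rule. Carried out as written, it raises the trial-wise false-stop risk under equal mortality from 0.099 to 0.20 and lowers the evidence needed to stop from LR 6.3, 4.0 or 3.3 to about 2.27 at every look.

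The null figures rest on the usual joint normal approximation for accumulating data and are confirmed by simulation across assumed mortality of 5% to 25%. The benefit and harm figures are illustrations under assumed rates. The effect on the simulated efficacy error rate and power was not quantified. SAP Section 2 and the protocol agree with each other and reproduce the stated 0.1, so the summary row is the outlier. It must be corrected.

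**What to change.** Replace the stopping-rule row in the SAP summary table with the Section 2 rule: at 150, 450 and 750 patients, stop if the one-sided likelihood ratio for higher mortality on plasma exceeds 6.3, 4.0 or 3.3 respectively, with a trial-wise false-stop risk of 0.1 under equal mortality. Delete the reference to significance at 0.1, and add a pointer to Section 2. State also that the simulated error rate and power were obtained under this rule, once the trial statistician has confirmed it. The cost is one row of SAP wording; no threshold, look or sample size changes.
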